In Session 1 (pre-medication baseline), we will collect baseline measures of smoking urge, withdrawal symptoms, mood, cognitive performance, a behavioral economics-based measure of cigarette demand and effects of smoking a cigarette on cigarette reward, satisfaction and mood. Next, participants will be randomized to VAR (1 mg twice daily for 3 weeks) or PLA, using urn randomization to stratify on gender and dependence. Participants will complete a week of medication use using the standard dose run-up (0.5 mg once daily on days 1-3, 0.5 mg twice daily on days 4-7, then 1 mg twice daily until the end of the medication period). In Session 2, which occurs after one week on medication, participants will complete the same laboratory assessments as in Session 1. Next, participants will undergo a 3-day abstinence period. They will come to the laboratory twice per day and will receive escalating cash incentives for breath carbon monoxide (CO)-verified abstinence. At each visit, cigarette craving and withdrawal symptoms will be measured. At Session 8 (Thursday morning), participants who have been continuously abstinent will complete the same procedure as in Sessions 1. For ethical reasons, participants who complete the study through Thursday and who wish to remain abstinent may opt out of smoking during this session and will still receive full compensation for participation, as long as they attend this lab session and complete the other session measures.

Participants will be asked to return to the laboratory on Friday morning. Breath CO will be measured and time of first lapse (single cigarette) and relapse (return to regular smoking) will be collected among those who have lapsed and relapsed. Those still abstinent ($CO \leq 4$ ppm) since Session 8 will receive a small cash incentive. Next, participants will be shown how to use breath CO monitors with smart phones to record

and text us videos of themselves providing CO samples twice per day for the following week to determine time to lapse and relapse. Participants will receive \$5 for each submitted sample (not contingent on CO level), paid when the smart phone and CO monitor are returned at the end of the week.

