A total of 48 randomized participants are planned for the R21 phase. This sample size is based on Aim 1, which is to determine effects of VAR versus PLA on smoking urges and negative affect during abstinence, reinforcing effects of a smoking lapse, cognitive function and time to relapse in SS. A repeated-measures design with 48 total participants provides 80% power to detect main and interaction effects on the primary targets (smoking urges and negative affect during abstinence) and secondary targets (reinforcing effects of a smoking lapse) of at least $d = .40$ in size, assuming a moderate within-subject autocorrelation. While this effect size is somewhat smaller than those detected by West et al. (2008) for effects of abstinence on urges and negative affect during abstinence and smoking satisfaction and reward from relapse (d 's = .32-.44), abstinence was not controlled or biochemically verified after target quit date in that study, and, as the authors noted, it is possible that the effects that they observed were due only to those who were completely abstinent. With our rigorous control of abstinence, which includes twice-daily CO testing and a stringent abstinence criterion, we believe that we will detect smaller effects. We are not determining sample size based on Aim 2 (which is to examine the extent to which the effects of VAR on time to relapse are mediated through its effects on the target mechanisms), but we should be able to

detect medium-sized group effects on latency to second lapse, and estimate the size of mediation relationships that would be detectable as significant. We anticipate 20% attrition between enrollment and randomization. Therefore, we anticipate needing to enroll up to 60 participants (30 per group) to include 48 in the intent-to-treat sample.

R33 phase:

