All data will be collected for research purposes only. All forms will be marked with only subject ID, session number and date. All records will be stored in locked files (physical or on computer) in locked rooms accessible only to research staff. Data gathered from people who attend the screening but do not meet inclusion criteria or decide not to participate will be stripped of personal identifiers or links and only the reason for study exclusion will be kept.

Personal information (participant name, address, telephone number, email address, locator contact information) must be collected so that the research assistant can contact people to schedule assessments, call with session reminders and arrange transportation to sessions. These data will be stored in a locked file that does not contain ID code numbers. All other data will be stored in files locked in a separate location with only code numbers identifying subjects and no personal identifiers. A cross-index of code numbers and participant names will be kept in a separate, password-protected computer file that is available only to research staff, PI, and mandated agencies during audits (e.g., study sponsor and Brown University IRB).

Saliva specimens for cotinine analysis will be marked with a study ID number, stored in the locked laboratory suite, and sent to a commercial laboratory for analysis. We will track samples sent and analysis results received using a form stored on a password-protected computer.

Data Analysis Plan

R21 phase

Variables will be examined for distributional assumptions associated with analyses to be used and transformed if necessary. Groups will be compared on demographic and other individual difference measures using t-tests for continuous measures and chi-square tests for categorical measures. Analyses of the effects of Group (VAR, PLA) and Time (Sessions 2-8) on QSU and MNWS-negative affect scores will be conducted using generalized estimating equation (GEE) models (Zeger et al., 1988), which allow for varying numbers of observations per participant (to minimize bias due to attrition) while controlling for autocorrelation (AR1 structure). GEE will also be used to analyze the effects of Group and Time (Screening, Sessions 2 and 8) on BPRS and other psychiatric symptom scores. Mixed 2 x 2 Analysis of Variance tests (ANOVAs) will be used to examine effects of Group and Abstinence (Sessions 1 and 8) on CEQ scale scores,

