Mediation of the relationship between group and lapse latency will be examined using an SPSS macro (Preacher & Hayes, 2004). Hypothesized mediators will include baseline Calgary scale, cognitive performance and Contemplation Ladder scores, Session 8 QSU and MNWS scores, Session 8 CPT and CEQ Reward and Satisfaction scores, and Session 8 cognitive performance scores. Simple mediator models will be used to investigate the direct effect of medication on relapse latency (c path) with no mediator in the equation, as well as the medication \rightarrow mediator path (a), the mediator \rightarrow latency path (b), and the effect of medication on latency with the mediator in the equation (c' path). The indirect effect of medication on latency via each mediator ($c - c'$) is equal to the product of the coefficients of the "a" and "b" paths (i.e., "ab"). If ab is not normally distributed, 10,000 bootstrap resamples will be used to obtain lower and upper 95% confidence intervals (CI) for each indirect effect (Preacher & Hayes, 2008). All variables will be standardized first so that path coefficients can be directly compared across variables with different metrics. In addition, step-wise regression will be used to examine whether screening BPRS scores (entered in Step 1) and Session 8 BPRS scores (Step 2) predict latency to relapse. The SPSS mainframe statistical package (SPSS, Inc., Chicago, IL) will be used for GEE, mediation and regression analyses. All other analyses will be conducted using SPSS Statistics Version 20 for Windows (IBM, Armonk, NY). Differences will be considered significant when $p \leq .05$.

R33 phase

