Following intent-to-treat principles, all randomized participants will be included in analyses. Baseline characteristics of the groups will be compared using ANOVAs for continuous variables and chi-square tests for categorical variables. CO levels from participants' videos will be averaged to provide a single CO measure for each week. Effects of the treatment groups on dependent measures (CO, total and consecutive abstinent CO samples, cigarettes per day, cotinine, QSU, MNWS, mood, CEQ, Stage of Change, Contemplation Ladder, cognitive scores (baseline co-varied), BPRS, Calgary Scale, AIMS, Simpson-Angus and BARS scores), will be analyzed with generalized linear mixed models (GLMMs) with Group (VAR + CM, VAR + NR, PLA + NR) as the between-subjects factor and Session as the within-subjects factor. We will examine main effects and the Group x Session interaction. This approach controls for correlations from repeated measurements and for person-level covariates. Baseline data will be imputed for missing. Differences will be considered significant when $p \leq .05$ and effect sizes will be calculated (Cohen, 1988). We will examine whether gender and FTND score (≤ 5 vs. ≥ 6) moderate treatment effects by adding these factors (separately) to each model. To examine whether reductions in smoking are mediated by changes in proposed targets, once the Group x Session GLMMs have been conducted, we will add concurrent QSU, MNWS and CEQ Reward and Satisfaction scores as covariates in these models to see the extent to which

smoking outcomes are attenuated by the mediators. We will use the same procedure to explore whether cognitive performance mediates smoking outcomes.

Feasibility outcomes include: median number of sessions attended, percentage of video samples submitted and percentage of those who indicate that they would be willing to participate in a longer CM trial. Responses to open-ended questions on the debriefing questionnaire will be described. Number and type of serious adverse events are expected to be rare so will be reported descriptively. Adverse event ratings will be analyzed individually using one maximum value over the 5 weeks for each person for each expected effect, including the baseline value of each item.

Quality Assurance

Procedures in place to ensure the validity and integrity of the data

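### The R21 primary model for urges and negative affect during abstinence has no abstinence rule, and unweighted AR1 GEE does not protect it against score-related loss

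*Combined protocol and SAP*

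**What the plan says.** The aims and the power section define the primary targets as urges and negative affect during abstinence. Primary and Secondary Outcome Measures names the QSU total and the MNWS negative affect score.

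The Data Analysis Plan (R21 phase) models both by Group and Time over Sessions 2-8 using GEE models, "which allow for varying numbers of observations per participant (to minimize bias due to attrition) while controlling for autocorrelation (AR1 structure". It gives no abstinence term, exclusion, weighting, imputation or sensitivity analysis for these scores.

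The Brief Description of Protocol places Session 2 after one week of medication and before the 3-day abstinence period. For the twice-daily visits in that period it says "At each visit, cigarette craving and withdrawal symptoms will be measured", without making abstinence a condition. Session 8 procedures are for participants who have been continuously abstinent. A rule exists for those who decline to smoke in Session 8, but none for those who smoke earlier.

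The power section shows that the issue was seen: of an earlier study it says "it is possible that the effects that they observed were due only to those who were completely abstinent". The section on DSMB monitoring activities leaves the handling of missing visits and data to the board. In R33, the same measures "will be analyzed with generalized linear mixed models (GLMMs").

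**The concern.** The analysis does not isolate the quantity that the aims name. A score taken after a cigarette is not a score during abstinence, and GEE cannot turn it into one. If such scores are absent instead, the loss is probably informative, because the Brief Description posits urges and negative affect as mechanisms of early relapse. Loss at Session 8 is built into the design. Unweighted GEE needs loss to be completely at random. If loss depends on earlier scores, it needs weighting or a correct correlation model. The stated reason for choosing GEE is therefore not supported.

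At stake is the size of the medication effect on both primary targets. The Session 8 QSU and MNWS scores also enter the mediation analysis, and the same targets feed the go/no-go decision.

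**Working it through.** **1. The plan's own figure.** Inputs from the power section: 48 randomized, taken as 24 per arm; d = 0.40; 80% power; moderate autocorrelation with no value given. The R21 analysis section sets p at .05 (two-sided assumed). For the mean of seven sessions with AR(1) correlation ρ:

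- v = [7 + 2 Σ(7−k)ρ^k]/49 for k = 1 to 6. At ρ = 0.3 (assumed), v = 11.776/49 = 0.240.
- SE = √(2v/24) = √0.0200 = 0.1415.
- z = 0.40/0.1415 − 1.96 = 0.867, so power = 80.7%.

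The 80% reproduces at ρ = 0.3. At ρ = 0.5 it is 65%, and at 0.7 it is 49%. It assumes complete data at all seven sessions. Enrolment also reproduces: 48/0.80 = 60. That allowance covers loss before randomization only.

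**2. Which modelled visits are abstinence visits.**

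- Session 2: not an abstinence visit, by design.
- Sessions 3-7: within the abstinence period, with no rule once a participant has smoked.
- Session 8: continuously abstinent participants only.

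If varenicline acted only during abstinence, a Group effect averaged over all seven sessions would be 0.40 × 6/7 = 0.343.

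**3. If post-smoking scores in Sessions 3-7 are kept.** With s the change in score after smoking and p the proportion who have smoked, the contrast at a visit is −0.40 + s(p_VAR − p_PLA). The documents give neither s nor p. Assume 33% VAR and 41% PLA by Session 8, so the gap is −0.08. At that full gap:

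- s = −1.0 gives −0.40 + 0.08 = −0.32.
- s = −0.3 gives −0.40 + 0.024 = −0.376.

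The gap is smaller at earlier visits, but the selective loss of lapsers at Session 8 adds to the bias. A simulation with both features, lapse driven by the last score and no Session 8 score for lapsers, gives −0.34 to −0.38 over Sessions 3-8 for s from −1.0 to −0.3. The loss is 0.02/0.40 = 5% to 0.06/0.40 = 15%.

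**4. If scores from the first smoking visit on are absent.** Under the same lapse model:

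- GEE-AR1 gives −0.38 to −0.40, a loss of 0-5%, and near none if the correlation is truly AR(1).
- A likelihood model gives about −0.40.

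Heavier and more unequal loss was also tried (abstinent at Session 8: 40-50% PLA, 56-80% VAR). With a truly exchangeable correlation, GEE-AR1 gave −0.33 to −0.38.

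**5. Other patterns** (separate runs, used for direction only):

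- Lapse equal in both arms and unrelated to urge, scores kept: −0.40, no bias.
- VAR lapsing more, scores falling after smoking: −0.41 to −0.48, inflated.
- PLA lapsing more, scores rising 0.5 SD after smoking: −0.42 to −0.45, inflated.

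**6. What the fix does to precision.** Covariance here is 0.5 person + 0.3 AR(0.5) + 0.2 noise, with lapse of 32-45% PLA and 25-34% VAR. Setting post-smoking scores to missing raises the SE from about 0.21-0.23 to 0.24-0.25. Power with scores kept versus set to missing:

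- 0.3 SD fall: 40% versus 36-38%.
- 0.6 SD fall: about 38% versus 37-38%.
- 1.0 SD fall: 33-35% versus 36-38%.

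**The case against.** A reader might infer that the plan counts post-smoking scores as abstinence scores. The documents do not say so. For Sessions 3-7 this is read from silence, and for Session 8 the protocol points the other way. A Session 8 contrast that includes lapsers' scores would therefore describe data that the stated procedure does not collect.

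A reader might also infer that the effect is diluted. That needs more lapse on placebo and a fall in scores after smoking. Both fit the plan's theory, but neither is quantified in it. Both arms are paid for abstinence, so lapse and the difference between arms could be small. If loss follows the last observed score and the correlation really is AR(1), as the plan specifies, GEE shows almost no bias.

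Nor can the bias be turned into a fall from the plan's 80% power. That figure reproduces only at ρ of about 0.3. Under the covariance in step 6, power at d = 0.40 is about 40% before any lapse, so the two cannot be combined.

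Three further points stand. Keeping all visits can be a legitimate treatment-policy estimand if declared. A likelihood model recovers the true value only when loss depends on observed scores. When lapse followed the current, unrecorded urge, it gave −0.37 to −0.39. And progression to R33 rests on a reduction of at least 20% in at least half the sample, not on the GEE p-value.

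None of this supplies the missing rule or supports the attrition claim. Leaving missing data to the DSMB does not define whether an observed post-smoking score belongs in the analysis.

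**Conclusion.** The point holds as an undefined estimand joined to an unsupported claim for GEE. The aims name scores during abstinence. The model includes one session that is certainly before abstinence, five with no rule after smoking, and one from which lapsers are removed. Loss is probably related to the scores, and unweighted AR1 GEE does not in general minimize the resulting bias.

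The bias is plausibly toward zero: about 5-15% of a 0.40 SD effect if post-smoking scores are kept, and about 0-5% if dropped. These sizes rest on the assumed lapse rates, lapse driven by the last score, and a 0.3-1.0 SD fall after smoking. Other patterns give no bias or inflation. The change is worth making because it is cheap and makes the result interpretable, not because it gains power.

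**What to change.** 1. For QSU and MNWS, replace GEE with a likelihood-based linear mixed model: Group, Time and Group × Time, with unstructured or person-plus-AR1 covariance. Treat Session 2 as a separate pre-abstinence time point and take the Group contrast over Sessions 3-8.
2. Use the CO result from each visit to mark the first non-abstinent visit. State the limit used, since a numeric one is given only for the Friday visit. Report the contrast with scores from that visit on set to missing, and beside it the contrast from all available visits. State in advance which is primary. Changing the model alone does not help, because kept post-smoking scores are observed values.
3. Add a not-at-random sensitivity analysis and report abstinence by arm and session.

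The cost is SAP wording and a few extra model runs on data already collected. R33 already plans mixed models. The downsides are a missing-at-random assumption, a somewhat larger standard error and little or no gain in power.

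### The R21 GEE for the primary targets leaves the variance estimator, reference distribution and Time coding open; with robust errors and categorical Time, the Group x Time test has about 12-14% false positives at 24 per arm

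*Combined protocol and SAP*

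**What the plan says.** The R21 part of the Data Analysis Plan examines Group (VAR, PLA) and Time (Sessions 2-8) on the two primary target measures by GEE. It gives two reasons: these models "allow for varying numbers of observations per participant (to minimize bias due to attrition"), and they do so while "controlling for autocorrelation (AR1 structure"). The same section sets the threshold: "Differences will be considered significant when $p \leq .05". SPSS is named, but no option within it.

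Under Power Calculation and Sample Size, "A total of 48 randomized participants are planned for the R21 phase". The arm size is not written out; 24 per arm follows from "we anticipate needing to enroll up to 60 participants (30 per group) to include 48 in the intent-to-treat sample". The design is said to be one that "provides 80% power to detect main and interaction effects on the primary targets", for effects of "at least $d = .40$ in size, assuming a moderate within-subject autocorrelation". The interaction is therefore a claimed result, although the GEE sentence itself lists only Group and Time.

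For R33, the outcomes "will be analyzed with generalized linear mixed models (GLMMs").

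Nowhere do the documents give the GEE variance estimator, a small-sample correction, a t or F reference, the coding of Time, or a value for the autocorrelation.

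**The concern.** GEE inference rests on large numbers of independent clusters, and here there are 48. The robust variance is estimated from 48 sets of residuals and, with a chi-square reference, is treated as known. That matters little for one contrast. It matters a good deal for a joint test of six, which is what Group x Time becomes if seven sessions are entered as categories.

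The alternative, a model-based variance, takes the AR1 structure as true. Craving scores may well carry a stable difference between people that does not fade over sessions. AR1 then understates the variance of a person's average, and so the standard error of the Group effect.

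These are the planned group tests of the primary targets over the abstinence period, and the sample size is based on the aim that they serve. With the choices open, the stated .05 may not be the error rate delivered, and the choices could be made after the data are seen.

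**Working it through.** **Inputs.** From the documents: 48 randomized, about 24 per arm (inferred), 7 sessions, threshold .05, d = .40, power 80%, AR1 working correlation. Assumed: two-sided tests, normal outcomes, unit variance per session, and correlations of .3, .5 and .7, because the plan says only moderate.

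**1. The plan's own figure.** Take the Group effect on the 7-session mean. Under AR1 the variance of that mean is [7 + 2Σ(7−k)ρᵏ]/49, k = 1 to 6. For ρ = .3 this is 11.776/49 = 0.2403, SD 0.490. Power = Φ(0.40/0.490 × √12 − 1.96) = Φ(0.867) = 0.807. The stated 80% is reproduced at ρ = .3. It is 0.652 at .5 and 0.486 at .7. The match therefore depends on a correlation the plan does not give.

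**2. Robust errors, categorical Time.** With complete data, equal arms and Group x Time fully specified, the GEE estimates are the cell means whatever the working correlation. The uncorrected sandwich for the six interaction contrasts is then the pooled covariance on 46 df, scaled by 46/24². The Wald statistic equals T² × 48/46, where T² is Hotelling's statistic and T² = (6 × 46/41) F(6, 41). Hence

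- Group x Time: P(T² > 12.592 × 46/48) = P(F(6, 41) > 12.067 × 41/276) = P(F > 1.793) = 12.5%.
- Group: P(F(1, 46) > 3.841 × 46/48) = P(F > 3.681) = 6.1%.

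The true correlation does not enter either result.

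**3. Model-based AR1 errors, Group test.** If the true correlation is exchangeable, the variance of the 7-session mean is (1 + 6ρ)/7, but the model uses the AR1 value from step 1.

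- ρ = .3: 0.400 against 0.240; 1.96 × √(0.240/0.400) = 1.519; two-sided error 12.9%.
- ρ = .5: 0.571 against 0.348; 1.96 × √(0.348/0.571) = 1.529; error 12.6%.
- ρ = .7: 0.743 against 0.518; 1.637; error 10.2%.

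No sample size appears in these ratios.

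**4. Simulation under the null.** 24 per arm, 7 sessions, 0% or 20% dropout (assumed), 2,000 trials per setting, and 8,000 trials without dropout for AR1 .5 and exchangeable .5. Wald chi-square tests, Time categorical:

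| True correlation | Robust: Group | Robust: Group x Time | Model-based: Group | Model-based: Group x Time |
|---|---|---|---|---|
| AR1 .3-.7 | 6.0-6.6% | 11.4-13.6% | 5.2-5.5% | 4.8-6.4% |
| Exchangeable .3-.7 | 5.7-7.2% | 11.6-14.4% | 9.8-13.8% | 3.8-5.8% |
| Random intercept (40% of variance) + AR1 .5 | 5.6-5.8% | 12.1-13.3% | 6.7-7.0% | 5.0-5.4% |

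Other random intercept plus AR1 settings gave 7.6-8.1% for the model-based Group test. With linear Time and a true AR1 of .5, Group and interaction were 6.5% and 6.0% (robust), and 6.0% and 5.1% (model-based).

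**5. Do the remedies work?** An unstructured covariance with an exact F test gave 4.9-5.4% for Group x Time and 4.8-5.2% for Group. A bias-corrected (Mancl-DeRouen) sandwich inflates each residual by 24/23, so the Wald statistic becomes T² × 23/24. With chi-square kept, P(F(6, 41) > 13.139 × 41/276) = P(F > 1.952) = 9.5%; simulation gave about 9-11%. Adding an F reference brought it to 3.4-5.5%, and Group to 4.0-5.0%.

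**The case against.** The strongest reply is that no single test fails under both standard errors. That is correct. A reader might infer that the primary-target tests run at 12-14% either way. The documents and calculations do not support this: the robust figure belongs to the interaction and the model-based figure to the Group test. The latter also needs a correlation that the plan does not assume, and no small-sample correction would cure it.

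Second, the 6-df test is an inference. The plan does not say that Time is categorical, and with linear Time the excess is slight, at least under AR1. This stands as a limit on the finding, and is itself a reason to state the coding.

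Third, a reader might infer that the decision to proceed to R33 is compromised. It is not. The rule in the Brief Description of Protocol is a reduction of at least 20% in at least 50% of the sample, and it involves no test.

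Fourth, the plan's reliance on GEE to limit attrition bias might look like a further fault. In simulations with 23-38% dropout, rates found nowhere in the documents, GEE-AR1 was only 0.02-0.04 SD closer to zero than a likelihood model for a true 0.6 SD effect. That is too small to press.

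Finally, R33 is a precedent only for the model family. Its mixed models state no small-sample degrees of freedom either.

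**Conclusion.** The point holds in a limited form. The plan does not fix what is needed to know the error rate of its primary-target tests. Under one common set of choices (categorical Time, robust errors, chi-square reference) the Group x Time test has about 12-14% false positives instead of 5%, and the Group test about 6-7%. This result does not depend on the unknown correlation; it assumes roughly normal outcomes and about 24 per arm.

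Under model-based AR1 errors the interaction is about nominal. The Group test is near 5% if AR1 is true, about 7-8% under a random intercept plus AR1, and about 13% if the correlation is flat at .3-.5. Those figures rest on assumed correlations. The linear-Time figures of about 5-6.5% were obtained only for a true AR1 of .5.

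What is at stake is how the R21 p-values are read, above all for an interaction that the plan claims to power. Progression to R33 is not at stake.

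**What to change.** Analyse QSU and MNWS negative affect with a linear mixed model for repeated measures, using an unstructured covariance or a random intercept plus AR1, with Satterthwaite or Kenward-Roger degrees of freedom. Alternatively, keep GEE with a bias-corrected sandwich and a small-sample F reference. Both parts are needed, since the corrected sandwich with chi-square still gives about 9-11% for the 6-df test. In either case, state how Time is coded, that Group x Time is in the model, and which effect is the main test.

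The cost is a few lines of SAP text, with no added visits or participants. P-values will be somewhat larger, mainly for the interaction: by step 2 of the working, an uncorrected robust 6-df result that just reaches .05 corresponds to about .125.

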cognitive measure scores (with baseline scores covaried), CPT demand indices and within-session changes (post- minus pre-smoking) in CO level and positive and negative mood scale scores. Significant interactions will be followed by simple effects tests. Those who opt not to smoke in Session 8 will not be included in the Group x Abstinence analyses of CEQ, or pre-to-post smoking changes in CO or mood, but will be included in all other analyses (only one SS opted not to smoke in Session 8 in our previous study, Tidey et al., 2014). Latency to relapse will be defined as hours between the start of Session 8 and time of relapse, collected in person at Friday's session and by videoed CO sample in the follow-up week. We will follow up for one week after Friday's session, which is 8 days after Session 8. Thus, the maximum latency until second lapse will be 192 h, at which point data will be censored. Lapse latencies will be compared in VAR vs. PLA using a t-test. We will examine whether gender and FTND score (≤ 5 vs. ≥ 6) moderate the effects of VAR by adding these factors (separately) to each model.

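### R21 tests the drug effect on the CEQ scales, CPT indices and within-session CO and mood changes as a change score; adjusting Session 8 for Session 1 would usually be more precise at almost no cost

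*Combined protocol and SAP*

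**What the plan says.** In the combined protocol and SAP, Data Analysis Plan, R21 phase, the rule that begins with the CEQ scale scores is: "Mixed 2 x 2 Analysis of Variance tests (ANOVAs) will be used to examine effects of Group and Abstinence (Sessions 1 and 8"). The sentence goes on to "cognitive measure scores (with baseline scores covaried), CPT demand indices and within-session changes (post- minus pre-smoking) in CO level" and in the mood scales. Baseline is thus covaried for the cognitive scores only, and this point leaves cognition aside. The follow-up rule is: "Significant interactions will be followed by simple effects tests".

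The R21 session description in the Summary of the Protocol fixes the timing: "In Session 1 (pre-medication baseline), we will collect baseline measures of smoking urge", and then "Next, participants will be randomized to VAR (1 mg twice daily for 3 weeks) or PLA". Session 8 comes after the three-day abstinence period, on medication.

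On size, "A total of 48 randomized participants are planned for the R21 phase". Power Calculation and Sample Size claims 80% power for main and interaction effects on the primary targets and on the "secondary targets (reinforcing effects of a smoking lapse) of at least" d = .40. It describes the within-subject autocorrelation only as moderate. Three CEQ scales (Satisfaction, Reward, Craving Reduction) appear under Primary Outcome Variables. Two more (Enjoyment of Respiratory Sensations, Aversiveness) are secondary.

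**The concern.** Session 8 is the only on-drug measurement in this two-session model, and Session 1 is a true pre-randomisation baseline. None of the model's three routes to a VAR versus PLA comparison uses that baseline well.

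- The Group x Abstinence interaction compares the arms on the raw change, which fixes the slope on Session 1 at 1 whatever the data show.
- The Group main effect averages a pre-drug score with an on-drug score, so it carries half of any Session 8 difference.
- The simple effect of Group at Session 8 ignores Session 1 and is reached only after a significant interaction.

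At stake is precision for planned Aim 1 comparisons in a small sample. That sample may shrink further: the full Session 8 procedure is for continuously abstinent participants, and those who opt out of smoking leave the CEQ, CO and mood analyses.

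**Working it through.** **Inputs.** 48 randomised. Equal arms of 24 are inferred from the enrolment statement ("we anticipate needing to enroll up to 60 participants (30 per group) to include 48 in the intent-to-treat sample"). Significance level .05 is from the plan; two-sided is assumed because the plan does not say. The Session 1 to Session 8 correlation r is not given, so .3, .5 and .7 are shown, with .9 as a limit. Equal SDs at both sessions are assumed first and then relaxed. All 48 are taken as analysed, which is optimistic for both tests.

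**The plan's own figures.** Enrolment reproduces: 48/(1 − 0.20) = 60. The 80% power cannot be confirmed, because neither r nor the meaning of d is defined.

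- A Group difference of 0.40 SD held constant over Sessions 2–8 with AR(1) r = .3 gives 79–80%. That is the QSU/MNWS analysis, not this ANOVA. At r = .5 it gives 63–65%.
- The two-session interaction with .40 read as Cohen's f = 0.20 (a 0.80 SD difference in change) gives 77% at r = .5 and about 80% at r = .53.
- The two-session interaction with .40 read as the Session 8 difference in SD units gives 27% at r = .5. Reaching 80% needs r of about .88.

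**Equivalence.** In a 2 x 2 mixed ANOVA the interaction F is the square of the t on change scores. A numerical check gave 1.0097 for both.

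**Variance of the VAR − PLA contrast**, in units of SD² x 2/n with n = 24 per arm:

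- change score: 2(1 − r), 46 df
- Session 8 adjusted for Session 1: (1 − r²) x 45/44, 45 df (the factor 45/44 is the cost of estimating the slope)
- Session 8 alone: 1

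Apart from the slope cost, the ratio of adjusted to change-score variance is (1 − r²)/[2(1 − r)] = (1 + r)/2. The change score is less precise than Session 8 alone when r is below .5.

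**Example at r = .5, difference 0.40 SD.** Change score: SE = √(1 x 2/24) = 0.289, noncentrality 0.40/0.289 = 1.39, power 27%. Adjusted: SE = √(0.75 x 45/44 x 2/24) = 0.253, noncentrality 1.58, power 34%.

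| r | (1+r)/2 | Power at 0.40 SD, change vs adjusted | Power at 0.80 SD, change vs adjusted | Total N for the change score to match 48 adjusted |
|---|---|---|---|---|
| .3 | .65 | 21% vs 29% | 63% vs 80% | 48/.65 ≈ 74 |
| .5 | .75 | 27% vs 34% | 77% vs 87% | 48/.75 = 64 |
| .7 | .85 | 42% vs 47% | 94% vs 96% | 48/.85 ≈ 56.5 |

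The last column ignores the small slope cost. The ANOVA's Group main effect has only 11–13% power for a 0.40 SD Session 8 difference over the same r. Simulated type I error was .048–.050 for both the change-score and the adjusted test.

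**Where the gain ends.** At r = .9 and 0.40 SD the powers are 86% vs 87%. With 24 per arm the variances meet where (1 + r)/2 = 44/45, that is r ≈ .96. With 12 per arm and r = .9 the tests tie at 55%.

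**Unequal SDs.** If the Session 8 SD is k times the Session 1 SD, the ratio is k²(1 − r²)/(1 + k² − 2rk). At r = .7, k = 1.2 gives 0.734/0.760 = .97 and k = 1.4 gives 1.00/1.00 = 1.00, so the gain is almost or entirely gone. A smaller Session 8 SD makes the gain larger.

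**The case against.** The planned test keeps its type I error, so this is a matter of efficiency and not of validity. That stands.

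A reader might infer that a better test here changes whether the project moves to R33. The documents do not support that. The go/no-go rule asks whether a target falls by at least 20% in at least 50% of the sample. It counts individuals, and no p-value from this model enters it.

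A reader might also infer that adjustment is unbiased and better at any correlation below 1. Neither follows. The precision claim depends on the SDs as well as on r. The unbiasedness claim needs the randomised groups intact, whereas Session 8 data come only from continuously abstinent participants and, for CEQ, CO and mood, only from those who smoke. In one assumed scenario there is no drug effect, r = .5, a stable trait lowers the chance of reaching Session 8, and retention is 89% vs 66% by arm. There the adjusted analysis showed a spurious difference of about .07 SD and the change score about 0. Other selection mechanisms could favour adjustment. This does not remove the efficiency gain, but it is a good reason to report both.

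Finally, d = .40 is not defined as a Session 8 difference, and the ANOVA also serves to test Abstinence, which a Session 8 model cannot do. Both points stand; the second shapes the fix.

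**Conclusion.** The point holds as one of efficiency. For these outcomes the planned drug-effect test is a valid change-score comparison. A Session 8 analysis adjusted for Session 1 is usually more precise. With 24 per arm and equal SDs the gain is 5 to 8 power points at a 0.40 SD Session 8 difference for r from .3 to .7. At 0.80 SD it runs from 17 points (r = .3) down to 2 (r = .7).

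The direction is well supported over that range. The size rests on an r and on equal SDs that the documents do not supply, and it is small at r of .8 or above or if Session 8 scores are more variable. Adjustment does not rescue the 80% claim: if .40 is the Session 8 difference, power is still only 29–47% for r from .3 to .7. Neither estimate is fully protected by randomisation, because of who supplies Session 8 data.

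**What to change.** For all CEQ scales, the CPT indices and the within-session CO and mood changes, take the VAR versus PLA effect from the model Session 8 score = Group + Session 1 score, and report the Group coefficient with its 95% CI. For the within-session outcomes, the score at each session is the post- minus pre-smoking change. For moderation, add gender or FTND category and its interaction with Group, one moderator at a time as now planned.

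Keep the Abstinence effect (Session 1 versus Session 8) as a separate within-subject test. Report the change-score comparison as a sensitivity analysis, and state that both analyses include only participants who supply Session 8 data.

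The cost is one error degree of freedom and SAP wording. Session 1 scores are already collected, so no extra participants or measurements are needed.
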